### Introduction

The aim of the National Foundation for Educational Research (NFER)'s evaluation of Graphogame Rime is to test the impact of the programme on pupils' reading skills. Graphogame Rime is a computer game developed to teach pupils to read by developing their phonological awareness and reinforcing the connections between phonological units and spelling units, highlighting rhyming connections. Originally developed by a Finnish University, the Graphogame group of computer programs employ algorithms that analyse a child's performance and constantly adjust the difficulty of the content so that the challenge matches the learner's ability.

The primary research question is whether playing Graphogame Rime as part of literacy lessons improves pupils' development of reading ability, compared to 'business as usual' participation in literacy lessons.

The NFER/Cambridge research team aims to answer this question by recruiting ten primary or infant schools to participate in the study and randomly allocating pupils each to one of two groups: a group of pupils that spend 10-15 minutes each day playing on the Graphogame

Rime computer games during literacy lessons and a 'business as usual' control group of pupils from the same classes who will have normal tuition in literacy lessons.

The University of Cambridge ('Cambridge') research team administered tests in literacy (New Group Reading Test (NGRT) – Level 1B) to selected year 2 pupils in all schools to measure literacy ability at baseline. The NFER research team has administered post-tests in literacy (NGRT – Level 1B) to the same pupils to measure the development of literacy ability.¹ The NFER research team have also administered a spelling test (Single Word Spelling Test) to measure the development of spelling ability.

The aim of the analysis is to measure the differential progress in literacy development between pupils in each group, and thereby measure the effect of the training programme and teaching materials when administered by teachers under typical classroom conditions.

# Sample size

The aim of the study was to recruit 10 Cambridgeshire schools and include year 2 pupils that had not reached the expected standard in the phonics screening check. Eligible pupils would then be randomly allocated to either the intervention or control group (see 'Randomisation'). The same design will be used for two years (2015/16 and 2016/17), doubling the overall sample size.

Initial estimates of statistical power suggested that a total sample size after two years of 400 pupils would be sufficient to detect a standardised effect size of 0.17 with 80% power. For sample size calculations, we assumed a final model without a school-treatment interaction and including a fixed effect for school. This is appropriate since we do not intend to generalise the results of the trial beyond its schools (Feaster et al, 2011). This effect size is smaller than might be expected of the Graphogame programme according to previous small-scale researcher-administered studies, but is appropriately conservative given that previous research had used outcome measures closely aligned to the intervention and that individual researchers sat with children and encouraged them to persist on task while they played Graphogame.

Cambridge was able to recruit 11 schools in the first year, from which 216 pupils were tested at baseline and allocated to a group. Given that we might expect up to 10 per cent attrition, this is in line with our expectations of the achieved sample size for the first year. We anticipate the sample size being similar in the second year of the study.

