### **Randomisation**

An NFER statistician performed a stratified randomisation of pupils by class with the aim of balancing the randomisation at class level (i.e. having equal numbers in intervention and control groups within each class) to aid delivery. We first put schools in a random order; within school we put classes in a random order; and within classes we put pupils in a

<sup>1 Use of the Level 1B test was a change to the original protocol. See 'primary outcome' section.

<sup>2 Assuming a two-tailed test with a 95% confidence level, number of schools=10, expected number of pupils per school=20, intra-school correlation=0 (pupil randomisation), correlation between pre- and post-test scores=0.8.

random order. The number of classes per school varied from one to three. The entire list was then allocated to control and intervention in turn: first pupil to control, second to intervention, third to control, and so on. The SPSS syntax used to randomise pupils in the first year is shown in Appendix 1, and similar syntax will be used in the second year.

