#### **Confidence intervals**

We will estimate a 97% confidence interval (see section on interim reporting, below) alongside the standardised effect size to give the precision with which the effect size has been estimated. The upper and lower bounds of the confidence interval will be calculated as the effect size plus/ minus the product of the critical value of the t-distribution and the standard error of the intervention group indicator coefficient estimated from the model.

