#### Interim reporting

An interim analysis will take place at the end of the first year on just the primary outcome. The interim results will be discussed with the EEF Grants Committee, with advice from the Evaluation Advisory Group if required, to determine whether or not the trial should continue. If there is substantial evidence of a positive effect of the intervention then the Grants Committee may advise to move to a larger effectiveness trial, while if there is evidence of negative effects then they may advise to stop the trial. However, the analysis of data from the first year will be underpowered for plausible positive or negative effects and therefore it is most likely that the trial will be completed as planned.

We will use the following rule to decide what to recommend on the basis of the interim analysis:

Interim result	Decision
Significant positive effect (p < 0.0294)	Expand to effectiveness trial
No significant effect (p > 0.0294)	Continue as planned
Significant negative effect (p < 0.0294)	Stop trial

Armitage et al. (1969) were the first to numerically compute the extent to which the type I error probability is increased over its nominal level if a standard hypothesis test is conducted at each of a series of interim analyses. They studied the problem of testing a normal mean with known variance and set the significance level (or type I error probability) for the trial to be 5%. If one interim analysis and one final analysis are performed this error rises to 8%. This is the situation here. Although the final result will not be predicated on a significance level, the decision at the interim analysis is binary and we should therefore adopt an appropriate threshold to aid our decision. The threshold p < 0.0294 is the Pocock boundary for two planned analyses (Pocock, 1977). Were the final analysis to use a significance threshold, it would also need to be p < 0.0294. We will hence construct 97% confidence intervals around the final result and note that any reference to the trial demonstrating a 'significant' result (at either analysis) is still at the conventional level of p < 0.05.

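### The stated 80% power for an effect of 0.17 assumes one two-sided 5% test and was not updated for the Pocock level of 0.0294, at which it is about 75%.

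*SAP*

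**What the plan says.** SAP, Sample size: "a total sample size after two years of 400 pupils would be sufficient to detect a standardised effect size of 0.17 with 80% power". The section calls this an initial estimate.

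SAP, footnote 2 (attached to that sentence), gives the basis: "Assuming a two-tailed test with a 95% confidence level, number of schools=10, expected number of pupils per school=20". It adds an intra-school correlation of 0 and a pre/post correlation of 0.8.

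SAP, Sample size, on recruitment: 216 pupils were randomised in year 1 and a similar number is expected in year 2. "Given that we might expect up to 10 per cent attrition, this is in line with our expectations" for the achieved sample.

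SAP, Interim reporting: the primary outcome is analysed after year 1 with p < 0.0294 as the decision threshold, the Pocock boundary for two analyses. For the final analysis: "Were the final analysis to use a significance threshold, it would also need to be p < 0.0294".

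SAP, Confidence intervals: "We will estimate a 97% confidence interval", with a cross-reference to the interim reporting rule.

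**The concern.** The power statement and the error-control rule sit at different significance levels. Footnote 2 uses 0.05 once; Interim reporting uses 0.0294 at each of two looks so that the overall error stays at 5%. A stricter level at each look costs power, and the SAP does not account for that cost.

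The 80% figure is the only statement of power for the full two-year trial. The SAP presents 0.17 as a deliberately conservative target, so a reader will take 80% for 0.17 as a property of the design. What is at stake is the accuracy of that description.

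**Working it through.** **Inputs, all from the SAP.** Total N = 400, effect 0.17 SD, two-sided 5% test, correlation r = 0.8, intra-school correlation 0 (Sample size and footnote 2). Allocation is alternating, so 1:1 (Randomisation). Level 0.0294 at each look (Interim reporting). Expected analysed sample: 2 × 216 × 0.9 = 388.8, about 389 (Sample size). The analysis uses pupils with both tests (Primary analysis).

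**Formulas.** Residual SD = √(1 − 0.8²) = 0.6. Standard error of the difference = 0.6 × √(4/N) = 1.2/√N. Power ≈ Φ(0.17/SE − z), where z = 1.960 for two-sided 0.05 and 2.178 for two-sided 0.0294. Minimum detectable effect at 80% power = (z + 0.842) × SE.

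**Step 1: reproduce the stated figure.** N = 400: SE = 1.2/20 = 0.060 and 0.17/0.060 = 2.833. Power = Φ(2.833 − 1.960) = Φ(0.873) = 80.9% (80.7% with the t distribution). Minimum detectable effect = 2.802 × 0.060 = 0.168. The N needed for 80% is 392. The SAP's figure is confirmed at 0.05.

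**Step 2: change only the level.** N = 400 at 0.0294: Φ(2.833 − 2.178) = Φ(0.655) = 74.4%. Minimum detectable effect = 3.020 × 0.060 = 0.181.

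**Step 3: the expected analysed sample.** N = 389: SE = 1.2/√389 = 0.0608 and 0.17/SE = 2.794. At 0.0294, Φ(0.616) = 73.1%, with a minimum detectable effect of 0.184. At 0.05 the same N gives 79.8%.

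**Step 4: count a positive result at either look.** The two test statistics are bivariate normal with correlation √0.5, assuming equal information per year. The interim mean is 0.17/SE × √0.5.
- N = 400: 43.1% cross at the interim and a further 33.5% at the final look, total 76.6%.
- N = 389: 42.0% + 33.4% = 75.4%.
- Check under no effect: overall error is 5.0% with 0.0294 at both looks, against 8.3% with 0.05 at both.

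| Pupils analysed | Power at 0.05, single test | Power at 0.0294, final look | Power at 0.0294, either look | Minimum detectable effect, final look at 0.0294 |
|---|---|---|---|---|
| 400 | 80.9% | 74.4% | 76.6% | 0.181 |
| 389 | 79.8% | 73.1% | 75.4% | 0.184 |

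**Step 5: split the loss.** At N = 400 the change of level costs 80.9 − 74.4 = 6.5 points at the final look, or 80.9 − 76.6 = 4.3 points over both looks. Going from 400 to 389 costs 1.1 to 1.3 points in every power column. For 80% at a single test at 0.0294, about 456 analysed pupils would be needed.

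**The case against.** **Nothing is miscalculated.** The stated figure reproduces, is labelled initial, and its assumptions are set out in footnote 2. That is true. The fault is that the figure was left standing beside a later rule it does not match, although the same section does update recruitment.

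**The final result is not tied to a significance level.** Interim reporting says so, and applies 0.0294 at the end only conditionally. This stands, and it limits how the finding may be worded: the level acts through the 97% interval and that conditional threshold. It does not remove the mismatch. The chance that a 97% interval lies wholly above zero at a true 0.17 is 74.6% with 400 pupils and 73.4% with 389 (level 0.03 in the formula above).

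**An early positive result is also an outcome of the design.** Agreed; the either-look figure of 75–77% is then the relevant one, and it is still below 80%.

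**Attrition may be lower than 10%.** The SAP gives 10% as an upper limit. If all 432 randomised pupils were analysed, power would be 77.8% at the final look and 79.8% over both. That is the best case, not the SAP's expectation.

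Some stronger readings are tempting but unsupported:
- *Attrition is a joint cause.* The SAP already allows for it, and alone it leaves 79.8% at the 5% level.
- *The correlation of 0.8 must be too high because pupils were selected as weak readers.* The SAP reports no observed value, and using the same test form before and after could work the other way.
- *A null result would be misread.* The reported 97% interval already carries the wider multiplier.
- *The boundary should be replaced.* Pocock is a valid pre-specified choice that holds overall error at 5%; another boundary is a trade-off, not a correction.

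**Conclusion.** The concern holds as an un-updated power statement. At the level the SAP adopts, power for 0.17 is about 73–74% at the final analysis and 75–77% over both looks, not 80%, and the minimum detectable effect is about 0.18 rather than 0.17. The chance of missing a true 0.17 at the final analysis is therefore about 26–27%, against the 20% implied.

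The figures rest on the SAP's own r = 0.8 and intra-school correlation of 0, 1:1 allocation, and 389 to 400 pupils analysed. The either-look figures further assume equal information in the two years and count a positive interim result as a success.

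A reader might infer that the trial is seriously underpowered or its analysis invalid. The SAP does not support that: the shortfall is modest, and the error control, estimate, interval and decision rule are unaffected. This is a correction of wording.

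**What to change.** Restate the power sentence in Sample size and the assumptions in footnote 2 at the level the plan uses, for example:

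> At the Pocock level of 0.0294, with about 389–400 pupils analysed and a pre/post correlation of 0.8, power for an effect of 0.17 is about 75–77% over both looks (about 73–74% at the final analysis). The minimum detectable effect at 80% power is about 0.18.

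The 5% single-test figure can stay beside it if it is labelled as the initial calculation made without the interim look. The cost is one sentence, one footnote and a slightly less favourable stated figure.

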### **Randomisation**

An NFER statistician performed a stratified randomisation of pupils by class with the aim of balancing the randomisation at class level (i.e. having equal numbers in intervention and control groups within each class) to aid delivery. We first put schools in a random order; within school we put classes in a random order; and within classes we put pupils in a

<sup>1 Use of the Level 1B test was a change to the original protocol. See 'primary outcome' section.

<sup>2 Assuming a two-tailed test with a 95% confidence level, number of schools=10, expected number of pupils per school=20, intra-school correlation=0 (pupil randomisation), correlation between pre- and post-test scores=0.8.

random order. The number of classes per school varied from one to three. The entire list was then allocated to control and intervention in turn: first pupil to control, second to intervention, third to control, and so on. The SPSS syntax used to randomise pupils in the first year is shown in Appendix 1, and similar syntax will be used in the second year.

#### **Outcome measures**

### **Primary outcome**

The primary outcome in the trial is pupils' test scores on the New Group Reading Test (NGRT) Level 1B. The original protocol stated that the primary outcome measure would be NGRT Level 2. A protocol amendment was made in March 2016 following the pre-test because we expected pupils to find the content in NGRT Level 2 too difficult, given how difficult they had found the pre-test.

The post-tests were (and will be in the second year) administered by NFER test administrators to ensure independence from the Cambridge research team that are delivering the intervention. Test administrators were not informed of which group each pupil has been allocated to and were advised not to discuss the interventions with teachers and to conduct the administration as they normally would. Post-testing for the first year of the evaluation took place during 11th – 25th April 2016.

We will use raw test scores (i.e. number of correct answers) rather than standardised or agestandardised scores for the analysis. The expected range of the scores is 0-43. We expect within-year age to be evenly distributed across the two groups since they have been randomised; processing the scores further would be of limited benefit for this research and might introduce ceiling or floor effects.

#### **Secondary outcomes**

A secondary outcome identified in the protocol will be used to test the secondary hypothesis that Graphogame Rime leads to an improvement in spelling ability. NFER test administrators will administer the GL Assessment Single Word Spelling Test A at the same time as NGRT and we will analyse the raw score.

# **Analysis**

#### **Overview and definitions**

This evaluation is an efficacy trial conducted within 11 schools in Cambridgeshire, many of whom are familiar with working with the developer. Schools were selected non-randomly and there is no intention of attempting to generalise the results of the trial beyond the participating schools. We are therefore in a situation of 'conditional inference' (Hedges et al, 2009); inferences are restricted to the particular schools in the study. This has considerable implications for the choice of analysis model. We shall model class as a fixed effect. Additionally, we will model the interaction between class and intervention as a fixed effect.

<sup>3 Randomisation was restricted by class rather than school – see 'randomisation' section.

There is considerable debate in clinical trials about how to report the main intervention effect when there is a significant site by treatment interaction (Feaster et al, 2011). For the purposes of this study, the main effect will be from a model without interaction terms i.e. the weighted mean of treatment effects across sites.

#### Standardised effect size

The coefficients of the statistical model are measured in terms of raw test score. As is standard for EEF evaluations, the effect size will be calculated as the coefficient on the intervention group indicator divided by the total sample standard deviation. We will apply Hedges' adjustment for small sample bias of estimated variance.

#### **Confidence intervals**

We will estimate a 97% confidence interval (see section on interim reporting, below) alongside the standardised effect size to give the precision with which the effect size has been estimated. The upper and lower bounds of the confidence interval will be calculated as the effect size plus/ minus the product of the critical value of the t-distribution and the standard error of the intervention group indicator coefficient estimated from the model.

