#### **Primary analysis**

The primary analysis of the impact of the intervention will be a regression model of reading test score at post-test including all data from both cohorts. The model will be estimated with all pupils that completed a pre-test and a post-test.

The primary outcome model will have raw score at post-test as the dependent variable and the following covariates will be included in every model:

- an indicator of whether the pupil is in the Graphogame intervention group. The
  excluded group is the control group, so the coefficient of the intervention group
  indicator measures the difference in (conditional) outcomes between the intervention
  group and the control group
- the pupil's raw score on the pre-test. The coefficient is incidental to the research, but explains a large proportion of outcome variance, increasing the power of the analysis.
- an indicator of which class and intervention cohort the pupil was in, to account for the stratified randomisation. As classes are nested within schools, an indicator for school is not necessary for this single-level model.

The above model will yield the main intervention effect for publication in the executive summary. In addition, a further model will explore the interaction between class and intervention in order to determine whether Graphogame was differentially effective between different classes or schools. This analysis will be somewhat underpowered but will yield interesting results in terms of whether certain classes or schools had larger effects than others.

The sample size and the rate of school and pupil attrition (i.e. the number of schools and pupils analysed compared to the number of schools and pupils that were randomised) will be reported in the CONSORT flow diagram. In an effort to determine whether there was any biased attrition, a summary of the analysed pupils' average characteristics will be reported by randomised group.

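### The confidence-interval formula adds a standard error in raw marks to an effect size in SD units, so the interval is too wide by a factor of the score SD

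*SAP*

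**What the plan says.** Three sections of the SAP fix the scales involved.

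- **Primary analysis:** "The primary outcome model will have raw score at post-test as the dependent variable".
- **Standardised effect size:** "The coefficients of the statistical model are measured in terms of raw test score", and "the effect size will be calculated as the coefficient on the intervention group indicator divided by the total sample standard deviation". The section adds: "We will apply Hedges' adjustment for small sample bias of estimated variance".
- **Confidence intervals:** "We will estimate a 97% confidence interval", to accompany the standardised effect size. The rule for the limits begins "The upper and lower bounds of the confidence interval will be calculated as the effect size plus/ minus the product", and that product is "the product of the critical value of the t-distribution and the standard error of the intervention group indicator coefficient estimated from the model".

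The coefficient is therefore rescaled to SD units before it becomes the centre of the interval. The standard error is taken directly from the raw-score model. No other section supplies a rescaling step for it.

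**The concern.** An interval whose centre is in SD units and whose half-width is in marks is not a confidence interval for either quantity. On a test where "The expected range of the scores is 0-43", the SD is almost certainly several marks, so the interval would be several times too wide.

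This matters because of the role the SAP gives the interval. The Sensitivity Analysis section makes the effect size and interval from the fixed-effects model without interaction the final word on the trial. The Interim reporting section says the final result will not hang on a significance threshold, and supplies 97% limits around it. A reader will judge the precision of the result from this interval. Applied literally, the rule would make a clear effect of the planned size look inconclusive, and the interval would disagree with the p-value from the same model.

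**Working it through.** **Inputs from the SAP.** Total N = 400, detectable effect 0.17 SD and 80% power (Sample size). Two-sided 5% test, pre/post correlation 0.8 and intra-school correlation 0 (footnote 2). 216 pupils allocated in year one, a similar number anticipated in year two, and up to 10% attrition (Sample size). Raw scores from 0 to 43 (Primary outcome).

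**Assumptions.** The score SD, S, is not given, so a range is shown. About 40 classes over the two cohorts is assumed for the degrees of freedom; 22 classes gives the same results to two decimals.

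**Step 1: reproduce the SAP's own figure.** Adjusting for the pre-test leaves a residual SD of sqrt(1 - 0.8²) = 0.6 SD. With 400 pupils split equally, the standard error is 0.6 × 2/sqrt(400) = 0.060 SD. The detectable effect is (1.960 + 0.842) × 0.060 = 0.168, which rounds to the stated 0.17. This standard error is therefore the one implied by the SAP's planning.

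**Step 2: the correct half-width.** At the expected analysed sample, 216 × 2 × 0.9 = 389 pupils:

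- SE in SD units = 0.6 × 2/sqrt(389) = 0.0608
- t critical value for 97% = 2.179
- half-width = 2.179 × 0.0608 = 0.133 SD
- 97% interval around 0.17 = 0.04 to 0.30

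At N = 400 the half-width is 2.179 × 0.060 = 0.131, and the interval is the same to two decimals.

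**Step 3: the half-width as written.** The model's standard error in marks is 0.0608 × S, so the half-width is 2.179 × 0.0608 × S = 0.133 × S. At 389 pupils:

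| Assumed S (marks) | SE in marks | Half-width as written | Interval around 0.17 |
|---|---|---|---|
| 3 | 0.18 | 0.40 | -0.23 to 0.57 |
| 5 | 0.304 | 0.66 | -0.49 to 0.83 |
| 8 | 0.487 | 1.06 | -0.89 to 1.23 |
| 10 | 0.608 | 1.33 | -1.16 to 1.50 |
| 12 | 0.73 | 1.59 | -1.42 to 1.76 |

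The ratio to the correct half-width is S in every row. If the correct limits also carry the Hedges factor J (about 0.998), the ratio is S/J, a difference of 0.2%.

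**Step 4: dependence on S.** For the interval as written to exclude zero at an effect of 0.17, S would have to be below 0.17/0.133 = 1.3 marks.

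**Step 5: conflict with the model's test.** An effect of 0.17 gives t = 0.17/0.0608 = 2.8, beyond the critical value of 2.179. The model's test would reject at the 3% level, while the interval as written would include zero at every S in the table.

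**Step 6: simulation.** With N = 400, 40 classes, S = 8, a true effect of 0.17 and 500 runs:

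| | As written | Rescaled |
|---|---|---|
| Mean half-width | 1.05 | 0.131 |
| Coverage | 100% | 97.2% |
| Interval includes zero | 100% | 24% |

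**The case against.** The strongest reply is that the sentence is shorthand. The section's stated purpose is to show the precision of the effect size, so the interval must be in SD units, and a competent analyst would rescale the standard error without being told. Limits of about ±1 SD would also clash visibly with the model's t and p-value, so the slip would probably be noticed. Nothing else in the trial depends on it: design, model, point estimate and the interim rule at p < 0.0294 are untouched.

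Much of this is fair. The harm is conditional on literal application, and the error concerns reported precision only. It does not rescue the text, however. The SAP specifies the division for the coefficient and omits it for the standard error, so correct reporting would depend on an unrecorded departure from the written rule, for the result the SAP treats as final.

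Three limits on the claim also stand.

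- The SD is assumed. Pupils were selected for not having met the phonics standard and found the pre-test hard, so a spread narrower than 5 marks is possible. Even S = 3 gives a half-width of 0.40.
- Inclusion of zero is shown for effects near the planned 0.17, not for every effect. At S = 5 an effect above about 0.66 would still exclude zero.
- Carry-over to the secondary analyses is an inference. The SAP says the FSM effect size is measured in the same way and that the spelling analysis reruns the primary models, but it does not restate the interval rule. FSM numbers and the spread of spelling scores are not given, so no figures are offered for them.

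**Conclusion.** The concern holds: the interval rule is wrong as written and must be corrected. The half-width is too large by a factor of the total-sample SD, apart from the 0.2% Hedges factor. With 389 pupils, a correlation of 0.8 and an assumed SD of 5 to 10 marks, it would be 0.66 to 1.33 where 0.13 is correct. The existence of the mismatch needs no assumption. Its direction (too wide) needs only an SD above 1 mark, and the conclusion that an effect of 0.17 would fail to exclude zero needs only an SD above about 1.3 marks. If the same rule is used for the FSM and spelling effects, each interval would be inflated by its own SD, so the widths would not be comparable with one another or with the primary result.

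**What to change.** In the Confidence intervals section, replace the rule with: limits = J × (b ± t × SE(b)) / S. Here b is the intervention coefficient, SE(b) its model standard error, t the critical value for the 97% interval, S the total-sample SD used for the effect size, and J the Hedges factor applied to the point estimate. Dividing SE(b) by S before forming the interval, with the same J, is equivalent. State that the rule also applies to the FSM and spelling effect sizes, each with the SD used to standardise that effect.

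The cost is a sentence or two of SAP wording. No new data, and no change to the design, the model or the interim rule, is needed.
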